The organization has not regularly engaged in clinical research and it is for this reason that they, along with Nexalin, sought out a partnership with the University of Penn Behavioral Sleep Medicine Program (Penn BSMP) and the Penn Human Subjects board to provide guidance and oversight with respect to the proposed protocol. The protocol was developed by investigators at Penn (Drs. [name] & [name]). All data acquisition, data management, and human subject oversight will be the sole province of the Penn collaborators. Carrier Clinic's role is to recruit subjects and to conduct the Nexalin treatment. Carrier Clinic personnel have extensive training and experience with brain stimulation via ECT and specific training from Nexalin regarding the safe and effective use of Nexalin based transcranial electrical stimulation (TES). Twenty eight members of the Carrier Clinic staff have attended a 75 minute training program. Each training was conducted by personnel from Nexalin (2 individuals) who collectively have 300 hours experience with the device and method (and have been certified by Nexalin re: the device use). Each training included lectures covering:

- 1) History of TES, how the method is similar and different from other related methods (e.g., TES vs. AV stimulation, Neurofeedback, TMS, and ECT, etc.), and
- 2) Procedures for use, and safety considerations.

This information was also made available via the provision of a treatment manual and a video. The trainings also entailed 6 hours of supervised hands-on training with the TES device (one treatment series for those that administer the intervention). At present, the CC has conducted TES as a regular intervention for patients in approximately 60 individuals cared for at the Carrier Clinic, since Octobet 2015. This translates to about 20 interventions with TES per week. Note: the Nexalin TES device has been cleared for clinical use since 2003 (See 510K FDA approval document and the device manual, Appendix 1) and it is estimated that the device is in regular use at 35 locations in the US and with about 7,500 patients treated to date.

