TES (as administered by the Nexalin apparatus) may be a viable alternative to ECT. A prior randomized, controlled trial compared antidepressant medication with Sham TES, Placebo with Nexalin at a lower dose, and Placebo medication with Nexalin at a higher dose. All three conditions showed remission of depressed mood by the end of treatment and maintenance of remission status following 12 weeks of follow-up. Thus, the effect sizes for Nexalin treatment were comparable to antidepressant medication. It should also be noted that the Nexalin device has undergone extensive safety analysis indicating that the device is safe for its intended use. Additionally, the classification of the device places it into a nonsignificant risk (low risk device) category. A review of Phase III Pivotal Clinical Trials (with a follow up period of one year) demonstrates that Nexalin TES Therapy does not result in any significant adverse events or side effects. In fact, there was no significant difference between reported events in the placebo group and reported events in the active treatment group.

[figure not shown]
Since the direct electrical stimulation represents a similar mechanism of action to ECT, and Nexalin has not only demonstrated effectiveness in depression but also has a much better safety profile than ECT, it is possible that Nexalin treatment could be a viable, more acceptable, alternative to ECT.

STUDY GOAL

Determine whether Nexalin TES is a viable alternative to ECT in subjects who do and do not accept ECT treatment.

STUDY DESIGN

A 2x2 factor Randomized Controlled Trial with block randomization. Inpatient subjects at the Carrier Clinic who are referred for ECT will be recruited, typed regarding their acceptance of ECT, and randomized to either treatment with TES or to a Sham condition. Treatment non-responders in either condition will continue as inpatients at the Carrier Clinic until they reach acceptable levels of functioning to be discharged. For additional details, see "procedures" section of this document.

STUDY DURATION

The study will last up to 2 years. This will allow sufficient time for recruitment and completion of all subjects.

TARGET POPULATION

Patients diagnosed with major depressive disorder (MDD) who have failed antidepressant therapy with one or more medications and are referred for ECT.

INCLUSION CRITERIA

To be included in the study, patients must be:

1. In-patients at the Carrier Clinic
2. Adults over age 18 and under age 65

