3. Able to speak, read and write fluently in English, assessed by the study coordinator at Carrier Clinic
4. Screened Negative for alcohol abuse and/or dependence
5. Able to provide informed consent, assessed by the study coordinator at Carrier Clinic
6. Referred for ECT
7. Not currently taking hypnotics or be prescribed hypnotics during the Nexalin trial.
8. Not pregnant or intending to become pregnant during the study
9. Committed to completion of the study.

TOTAL SUBJECTS ENROLLED

150

VULNERABLE POPULATIONS

No vulnerable populations (as defined by socio-economic status, geography, gender, age, disability status, and other populations identified to be at-risk for health disparities) will be recruited.

RECRUITMENT & RANDOMIZATION

As noted above, patients will be directly recruited from, and receive treatment at, the Carrier Clinic. Currently, the Carrier Clinic treats approximately 1,000 unique patients who receive ECT annually, resulting in 5,200 procedures performed per year. Randomization will occur in blocks, such that for every 20 subjects enrolled, 10 will receive Nexalin and 10 will receive Sham treatment.

COMPENSATION

No financial compensation will be provided to participants for participation in the trial.

PRIMARY OUTCOMES

Percent responders and non-responders to TES treatment or Sham TES treatment (who accepted or refused ECT) as assessed with the PHQ-9 (50% reduction or a score below 10).

SECONDARY OUTCOMES

Assess whether Nexalin TES produces significantly greater gains than Nexalin Sham for

1. Depression severity (as assessed with the PHQ-9, and the QIDS)
2. Anxiety severity (as assessed with the GAD-7 and the POMS)
3. Insomnia severity (as assessed with the ISI)

Finally, we will (post hoc) assess which baseline subject characteristics differentiate between responders and non-responders.

PROCEDURES

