All patients referred for ECT and otherwise eligible for the study will be approached by the Carrier Clinic study coordinator (or his designate) and asked whether they wish to participate in the research study. All subjects will be non-responders to traditional medical approaches (patients diagnosed with MDD who have failed antidepressant therapy with one or more medications). Those that express interest will review the study protocol with the study coordinator. The study coordinator will ascertain eligibility, address any concerns, and obtain written informed consent. Following the obtention of informed consent, the subject will be scheduled (or undergo at the time) a baseline assessment. The subjects that volunteer, are eligible, and are consented for the study will be queried as to whether or not they are willing to receive ECT. This decision will be used to type each subject that consents to be in the protocol (Accept or Refuse ECT). Following randomization to one of two conditions (TES or Sham), treatment will occur twice daily (40 minutes per session, separated by 5 hours' time between the AM and PM sessions) over 3-10 days. Subjects that do not exhibit 20% attenuation of symptoms (as assessed by an AM and PM version PHQ-9) on or before 6 treatments will be designated treatment non-responders and discontinue their participation in the study while remaining as inpatients at the Carrier Clinic. Note: During the Nexalin trial, all subjects will receive standard inpatient care where the only difference in the treatment regimens are that they are receiving TES or Sham TES in place of ECT. See "Protection Against Risks" section for stopping rules during treatment for subjects who do not show sufficient treatment response.

Session Protocol. The protocol for receiving treatment will be as follows:

1. Inpatients that have enrolled in the study will receive TES or Sham TES once in the AM and once in the PM.
2. The procedure will be conducted in a semi-private room while the subject reclines in a lounge chair.
3. The two TES session will each be 40 minutes in duration, separated by 5 hours' time.
4. The TES provider will oversee the administration of the patient on-line questionnaires.
5. The TES trained provider will complete the Carrier Clinic staffforms.
6. When the TES session is complete, the subject will resume his/her regular clinic activities.

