Treatment. As noted above, Nexalin TES or Sham TES will be administered twice per day (9am noon and then again 2pm-5pm), Monday through Friday, over the course of 3-10 days. Each patient will receive a minimum of 6 treatments and may receive up to 20 treatments depending on whether an adequate treatment response is observed during the first 6 session (this is based on the assessments overseen by the Penn staff based on the AM/PM PHQ-9 evaluations). All procedures will be performed at the Carrier Clinic facility by licensed

personnel with experience providing care to medication non-responders and will be specially trained on using the Nexalin equipment. Nexalin TES involves placing three conductive pads on the head (one on the forehead and one behind each ear). The patient then sits as the device administers the current through the pads. The waveform generated by the Nexalin device is a high frequency square wave (100 kHz), which has its amplitude modulated at a frequency of 77.5 Hz. Amplitude of the waveform (square wave pulse) is controlled to range from 0 to 4 mA peak current (off is 0 mA and on is 4mA). Each treatment session will last for 40 minutes. The treatment is not expected to be painful, but some individuals may experience discomfort (i.e. tingling and burning). In most cases, patients cannot feel when the pads are activated. The Sham treatment will be identical with the exception that there will be no current through the electrodes. Since the Nexalin treatment is undetectable, this will exactly mimic active treatment.

Assessments. Assessments will be made at baseline (pre-treatment), twice daily, once daily, and once every 3 days (6 sessions). All assessments will be administered on-line via two web-sites dedicated to the study (1 website for the subjects and one website for the clinical staff). The subject web-site will contain 10 questionnaires. The staff website will contain 5 forms.. See figure below for a specification of the specific instruments and schedule of administration. The site itself will be built using Research Electronic Data Capture (REDCap) software. Note: All data acquired via this method (raw and summary data) will not be available to the Carrier Clinic collaborators during the study.

	#	Instrument	Time Required	Baseline	Each Session	Q 3 days	Pre-Post	PRN
Patient	1	Demographics	5 min	●				
	2	AFQ & CAGE	2 min	●				
	3	Patient Expectancy	1 min	●				
	4	QIDS	5 min	●		●		
	5	ISI	2 min	●			●	
	6	SAFETEE	5-10 min	●		●		

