1. Patient Enrollment Form / Candidate Screener / Enrollment Form (completed once per week per patient): This requires the staff member to profile the patient who has been approached to participate in the study and to document if they meet eligibility and have been consented.
2. Procedure Tracking form / Patient Tracking (once per session): This requires the clinician to record: the patient initials; the patient PNC ID; the date of the session; the session #; the time session was conducted; the room the session was conducted in; the identifying sticker attached to the device; the device number; whether each instrument was administered; any comments they may have about the session; whether the

patient was diagnosed with any new disorders (and if yes, please list); and whether the patient's meds have been changed (and if yes, please list).

3. Adverse Event Form (*completed as needed*): This requires the clinician to record: the patient initials; the patient PNC ID; the date of the session; description of event; information about the event onset; start date and start time of event; information about the event offset; end date and end time of event; actions taken or treatments given; the severity of the event; event symptoms; diagnostic results; information about outcomes; and if the event is on-going what additional steps are planned.

4. Clinician Information Form (*completed once*):

This requires the clinician to record: the study clinician identification number, the clinician's name, the clinician's position at the clinic, the clinician's credentials (degree), and the clinician's contact information.

5. SBJ d/c Form (*completed as needed*):

This requires that a staff member specify that a subject has been withdrawn from, or quit, the protocol and the reason for why the subject is no longer participating.

ANALYSIS PLAN

The primary analysis for the study will be an evaluation of treatment response rates using an analysis of 2x2 contingency tables, using the Cochran-Mantel-Haenszel test to assess differences in treatment response by randomization groups, stratified by patient choice. The secondary analysis will evaluate how treatment non-responders and responders differ with respect to the various demographic and clinical profile measures.

CONFIDENTIALITY

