Transcranial electric stimulation devices are classified as a Class III device. These types of devices have been used for many years and occasional adverse effects have been reported, including: headache, nausea, minor burns, increased agitation, minor rash from specific electrodes, and electrical discharge when electrodes are removed. Specifically, headaches and nausea have been noted when current levels are higher than those used in the present study. Note: the device settings for current and duration of treatment are fixed (i.e., cannot be altered by the administering clinician or technician).

Risks associated with Sham treatment:

Since the sham treatment is identical except for a lack of active electrical current, the only risks include those associated with nervousness about the procedure and skin irritation from electrodes, described above.

Risks associated with questionnaires, interviews, and physical measurements:

As the subjects in the study are psychiatric patients with relatively significant symptoms, and the assessment measures directly address some of these symptoms, it is possible that answering questions in an interview format or in a questionnaire format can arouse uncomfortable feelings or even some level of distress. Although this is very rare, it is possible.

Risks associated with loss of confidentiality:

There is a possibility that records associated with the study (particularly paper documents such as those in the study binder) will inadvertently be seen by Carrier Clinic personnel that are not affiliated with the study.

Risks associated with ECT

While there are risks associated with ECT treatment, the provision of this therapy occurs outside the proposed protocol and therefore is not a risk of the proposed study.

PROTECTION AGAINST RISKS

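### The protocol prints a fixed block of 20 for the one clinic that recruits, consents and treats, with no described list concealment or operator masking; if earlier arms become known, the next can be guessed about 61% of the time

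*Combined protocol and SAP*

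**What the plan says.** Study Design describes "A 2x2 factor Randomized Controlled Trial with block randomization". Recruitment & Randomization gives the rule: "Randomization will occur in blocks, such that for every 20 subjects enrolled, 10 will receive Nexalin and 10 will receive Sham treatment". Total enrolment is 150.

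On roles, the introductory text says "Carrier Clinic's role is to recruit subjects and to conduct the Nexalin treatment". Procedures adds, of the clinic's coordinator, "The study coordinator will ascertain eligibility, address any concerns, and obtain written informed consent". The same section says that every eligible patient referred for ECT will be approached, and places consent, baseline assessment and ECT typing before randomized treatment.

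On masking, Procedures (Treatment) says "The Sham treatment will be identical with the exception that there will be no current through the electrodes" and describes the sham as indistinguishable from active treatment, while noting that some patients may feel tingling or burning. Procedures (Assessments) keeps study data from the clinic during the trial. The Procedure Tracking form, which clinic staff complete at each session, records "the identifying sticker attached to the device; the device number". Potential Study Risks says "the device settings for current and duration of treatment are fixed" and cannot be changed by the operator.

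The protocol text does not say who generates or holds the list, how an arm reaches the clinic, whether the operator is masked, or whether device identifiers differ by arm.

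**The concern.** With a fixed and published block, anyone who knows the earlier arms can tell which arm is behind and, late in a block, sometimes what must come next. Here the people who could acquire that knowledge work where patients are approached, judged eligible and consented. Possible routes are the device identifiers, what patients say they feel, and the skin check at the electrode sites described in Protection Against Risks.

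If the guess affects who enters, or when, the arms differ in prognosis before treatment starts. The planned Cochran-Mantel-Haenszel test adjusts only for ECT choice and cannot remove such a difference.

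**Working it through.** **Inputs from the protocol.** Block of 20, 10 per arm (Recruitment & Randomization); 150 patients (Total Subjects Enrolled); one clinic recruiting and treating (introductory text, Procedures). A single list is assumed, because the protocol does not say whether blocks run within ECT choice.

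**Assumptions, not in the protocol.** All earlier arms known; response 40% in both arms; two-sided 5% test; a gap of 10 or 20 percentage points in response probability between patients steered towards TES and towards Sham. The protocol states no alpha, power or response rates, so there is no plan figure to reproduce.

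**1. Guess rate in a full block.** Always guess the arm that is behind (toss a coin when level). For a block of 2m, expected correct guesses = m + (4^m / C(2m, m) − 1)/2. With m = 10: 4^10 = 1,048,576 and C(20,10) = 184,756, ratio 5.676. Then 10 + 4.676/2 = 12.34, and 12.34/20 = **61.7%**.

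**2. Over 150 patients.** 150 = 7 × 20 + 10. Exact recursion gives 5.47 correct in the first 10 places of a block. Total = 7 × 12.338 + 5.474 = 91.84, and 91.84/150 = **61.2%**.

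**3. Certain allocations.** Per full block, 2m/(m + 1) = 20/11 = 1.82. The final ten places add none, because one arm must first use all ten of its places. Total = 7 × 1.818 = **12.7 of 150**. Unlike the guess rate, this needs knowledge of the block size.

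**4. If earlier arms are unknown.** The guess rate is 50% at any block size.

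**5. Bias if every patient is steered.** Bias = (2g − 1) × gap, with g = 0.6123, so 2g − 1 = 0.2245. A 10-point gap gives 2.2 points; a 20-point gap gives 4.5 points.

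**6. Two-sided type I error.** Simulation of 150 patients in blocks of 20, no true effect, comparing two proportions without the ECT stratification:

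| Steering | 10-point gap | 20-point gap |
|---|---|---|
| None | about 5% | about 5% |
| Half of patients | about 5.3% | about 6.1% |
| Every patient | about 6% | about 8.5% |

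Repeated runs agree to within about 0.3 of a point. With an assumed 30% response instead of 40%, full steering gives about 6% and 9%.

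**7. Alternatives, earlier arms still known.** Share guessed correctly by following the arm that is behind:

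| Scheme | Correct |
|---|---|
| Fixed block of 4 | 70.8% |
| Random blocks of 4, 6, 8 | 68.0% |
| Fixed block of 10 | 65.3% |
| Random blocks of 16, 20, 24 | 61.3% |
| Fixed block of 20, over 150 | 61.2% |
| Big-stick rule, limit 6 | 53.8% |

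Under the big-stick rule (a fair coin unless the arms differ by 6, then forced), full steering gives a bias of about 0.8 or 1.6 points. About 11.5 of 150 allocations are forced.

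**The case against.** The strongest reply is that nothing in the protocol says clinic staff know the arms. The sham is described as matching, and the clinic is kept out of the study data. A reader might infer that staff can in fact predict the next arm and will choose patients accordingly. The documents do not support that: prediction above 50% depends on learning earlier arms, and no text shows that this happens or that anyone would act on it. Nor is it established that sham is built into particular devices. The fixed-settings statement points that way, but Protection Against Risks has the technician lowering the current when needed. Those two passages must be reconciled, and neither settles whether the operator is masked. The matching claim concerns what the patient experiences, and the data restriction covers questionnaire and form data in REDCap; neither amounts to allocation concealment.

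Second, all eligible patients are to be approached, and consent and ECT typing precede randomization. This limits steering. It does not remove it, because timing, ability to consent and commitment to completing the study remain clinic judgments. The clinic treats about 1,000 ECT patients a year, against 150 places over up to two years.

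Third, 20 is a large block and harder to predict than smaller ones. That is correct. Hiding the size removes knowledge of the certain allocations but not the advantage of counting; concealment and operator masking matter more. The big-stick rule is one choice among several and also forces some allocations.

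A reader might also infer a flaw from 150 not being a multiple of 20. It has no practical consequence: the worst split is 80:70, with relative efficiency 4 × 80 × 70/150² = 99.6%.

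**Conclusion.** The concern holds in conditional form. The protocol discloses a fixed block to the clinic that recruits, consents and treats, and its text does not show that operators are masked or that the list is kept away from that clinic. If earlier arms leak, about 61% of allocations can be guessed and about 12.7 of 150 are certain; if they do not, guessing is at chance.

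The false difference of about 2 to 4.5 points and the two-sided type I error of about 6% to 8.5% are an upper bound. They rest on full knowledge of past arms, steering of every patient in favour of TES, an assumed 40% response and an assumed prognostic gap of 10 to 20 points. With half the patients steered, the error is about 5.3% to 6.1%. The expected harm is modest, but it could not be repaired in the analysis and is cheap to prevent.

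**What to change.** - Delete the block size from the protocol and from every document the clinic holds.
- Have Penn generate and hold the list, using an undisclosed scheme that is not a fixed block. A big-stick rule is one option. Random blocks of 4 to 8 are not advised, because simple counting then guesses about 68%.
- Release each arm centrally through REDCap, which Penn already runs, only after eligibility, consent and ECT type are locked.
- Code the devices so that neither number nor sticker reveals the arm, and state whether the operator is masked.

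The cost is a revised protocol passage, a new allocation table, a release step in REDCap and recoded device labels. No extra patients are needed. The final split may be slightly uneven: under a big-stick limit of 6 it is at worst 78:72, with relative efficiency 4 × 78 × 72/150² = 99.8%.

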5. ISI (Completed at baseline and at the end of treatment): The Insomnia Severity Index is a brief insomnia screening tool that is the gold standard for quantifying severity of clinical insomnia symptoms. This will be administered at the beginning and end of treatment (e.g., 1st and 10th session).
6. SAFTEE (completed once every 3 days): The Systematic Assessment of Treatment-Emergent Effects was developed by the NIH to comprehensively catalog any physical symptoms experienced during psychiatric clinical trials along 16 subscales. This measure will be used to systematically measure symptoms and symptom categories.
7. PHQ-9 (completed in the AM and PM session): The Patient Health Questionnaire 9 is a brief, well-validated screening tool for depression. It has shown good reliability and validity for likely depression diagnosis and provides a means of assessing depression severity. The instrument in the present study has been modified so that it may be 1) administered twice daily and 2) used to track nightly sleep via 4 sleep related items
8. GAD7 (completed at baseline and once every 3 days): The Generalized Anxiety Disorder 7 questionnaire is a brief global screening measure of anxiety. It is well validated and is a standard screening tool for anxiety. This scale will allow for separate characterization of anxiety symptoms in addition to depression.
9. POMS (completed at baseline and once every 3 days): This is a 37-item adjective checklist where each item is rated on a 0-4 unipolar scale that ranges from not-at-all to extremely. The scored instrument provides values for six constructs including: tension-anxiety; depression-dejection; anger-hostility; fatigue-inertia; vigor-activity; and confusion-bewilderment. The outcome variables are measured in terms of the 6 factors and a total score, which are arrayed as T-Scores (standardized means of 50 +/-10).
10. “Faces” Mood Rating Scale (completed daily pre-post to each TES session): This is a single item 7 point bipolar rating scale for mood (from very happy to very sad). The measure is arrayed from -3 to +3.

Clinician Measures. All the clinician instruments to be used in the study are listed below along with their administration schedule and brief explanation regarding what the instrument measures

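### The primary response rule lets a PHQ-9 below 10 count on its own with no minimum baseline, and the Analysis Plan does not say which responder label, or which reading, enters the CMH test

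*Combined protocol and SAP*

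**What the plan says.** Primary Outcomes compares the percentage of responders, "as assessed with the PHQ-9 (50% reduction or a score below 10"). The two limbs are alternatives. Neither Target Population nor any of the nine Inclusion Criteria sets a depression score; entry rests on an MDD diagnosis, at least one failed antidepressant and referral for ECT.

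Procedures applies a second rule during treatment. Patients need a 20% fall in symptoms, "as assessed by an AM and PM version PHQ-9". Those who have not reached that mark "on or before 6 treatments will be designated treatment non-responders and discontinue their participation in the study". Between 6 and 20 treatments may be given, depending on early response.

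Assessment of Subject Clinical Status says that the PHQ-9 "has been modified so that it may be 1) administered twice daily and 2) used to track nightly sleep via 4 sleep related items". It does not say how the modified form is scored.

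The Analysis Plan evaluates response rates "using the Cochran-Mantel-Haenszel test to assess differences in treatment response by randomization groups, stratified by patient choice". It continues: "The secondary analysis will evaluate how treatment non-responders and responders differ with respect to the various demographic and clinical profile measures". Secondary Outcomes similarly plans to "assess which baseline subject characteristics differentiate between responders and non-responders". None of these sentences refers back to either definition or names the reading at which response is classified.

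**The concern.** A responder endpoint should identify patients who improved. Here the below-10 limb can be met at entry and kept with no change, or even after worsening: a patient who goes from 5 to 9 is a responder as the rule is written.

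The term non-responder also has two meanings. Three readings of the plan are possible:

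- **Primary Outcomes alone.** This is the natural reading, because the definition stands under that heading. The 20% check then only decides continuation, and unimproved low-baseline patients count as responders.
- **The 20% designation alone.** This is strained, because the written primary rule would not be the one analysed.
- **Both in sequence.** Patients stopped at the 20% check stay non-responders, and the rest are classified by the Primary Outcomes rule.

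The same data can give different response rates under these readings. If the choice is left open until data are seen, the primary result depends on it.

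**Working it through.** **Minimum fall that counts as response.** Assume one whole-number PHQ-9 total on the standard 0–27 range (the documents give no range for the modified form). For baseline b:

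- Rule as written: min(ceil(b/2), max(0, b − 9)).
- Rule with a 20% condition on the below-10 limb: min(ceil(b/2), max(b − 9, ceil(0.2b))).

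| Baseline | As written | With 20% condition |
|---|---|---|
| 1–5 | 0 | 1 |
| 6–9 | 0 | 2 |
| 10 | 1 (10%) | 2 |
| 11 | 2 (2/11 = 18%) | 3 |
| 12 | 3 (25%) | 3 |
| 13 | 4 (4/13 = 31%) | 4 |

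From 12 upward the two rules agree.

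**Where the two labels collide.** If one score feeds both rules, a single reading can be a response and also a fall of under 20% only at baselines of 11 or less (for example 9 to 9, 10 to 9, 11 to 9). That limit depends on scoring that the plan does not give. If both the AM and the PM reading had to show 20%, a patient entering at 12 with AM 10 (2/12 = 17%) and PM 9 (3/12 = 25%) would fail the check and still respond on the PM score.

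**What the sequential reading leaves.** Baseline 9, falling to 7 by treatment 6 (2/9 = 22%), passes the check. If the score returns to 9 by the end, the patient is a responder with no net change. Most of the problem goes, but not all.

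**Illustrative size.** The documents give no baseline distribution, response rates or power calculation, so every clinical input here is assumed: mean baseline 15, 17 or 20, SD 4.5; mean fall 5 (sham) and 8 (TES); endpoint SD 6; baseline–endpoint correlation r of 0.3 or 0.6; bivariate normal scores, rounded and limited to 0–27; one endpoint reading; 75 per arm (150/2). The share entering below 10 is Φ((9.5 − mean)/4.5): 11% at 15, 5% at 17, 1% at 20.

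Response in sham/TES, %, with unstratified two-proportion power at two-sided 5%:

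| Mean, r | As written | With 20% condition | 50% reduction only |
|---|---|---|---|
| 15, 0.3 | 48.4/68.1 (69%) | 45.0/65.3 (71%) | 34.7/55.2 (71%) |
| 15, 0.6 | 47.8/68.1 (71%) | 44.8/66.4 (77%) | 32.6/55.9 (83%) |
| 17, 0.3 | 36.8/57.0 (70%) | 35.3/55.7 (71%) | 28.5/48.1 (70%) |
| 17, 0.6 | 35.8/56.8 (74%) | 34.4/56.0 (76%) | 25.8/48.0 (81%) |
| 20, 0.3 | 23.1/41.4 (67%) | 22.8/41.0 (67%) | 20.1/37.6 (66%) |
| 20, 0.6 | 21.2/40.3 (72%) | 20.9/40.1 (73%) | 17.0/36.0 (76%) |

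Responders with no fall are 0.1–2.0% of sham and 0.1–1.6% of TES. Patients carrying both labels are 0.3–3.4% of sham and 0.2–2.8% of TES; at the high end that is 75 × (0.034 + 0.028) = 4.65 of 150. The risk difference is 18.3–21.0 points as written and 18.2–21.7 with the condition. It widens in five of the six scenarios and narrows by 0.1 point in one (mean 20, r 0.3).

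**The case against.** The strongest reply is that the plan is clear enough and the problem rare. The only definition under Primary Outcomes is the 50%-or-below-10 rule, so that rule governs. Alternatively, an ordinary reader applies both rules in sequence, and a patient who enters at 9 and never improves is stopped and stays a non-responder. Either way, few inpatients who have failed medication and been referred for ECT will enter below 10.

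Much of this stands. The Primary Outcomes rule is the natural reading, the sequential reading is reasonable, and the number affected may be very small. But the natural reading is the one under which unimproved patients count as responders, the sequential reading is not written down, and nothing in the eligibility criteria excludes low-baseline patients. The unstated reading and score also affect the classification of every patient, not only those with low baselines.

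A reader might infer more than the documents support:

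- **That the rule favours TES.** It is identical in both arms.
- **That it costs the trial much of its power.** If 10% entered at 9 or less and all counted as responders in both arms, assumed rates of 30% against 50% would become 37% (0.10 + 0.90 × 0.30) against 55% (0.10 + 0.90 × 0.50), and power at 75 per arm would fall from 70.9% to 60.1%. No document supports that share, or response in all such patients.
- **That 3.4% bounds the double-labelled share.** It holds for one score feeding both rules; different AM/PM scoring could raise it.

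**Conclusion.** The point holds as a gap in the definition of the primary endpoint. As written, response does not require improvement at baselines of 9 or less and requires under 20% at 10 and 11. The plan does not state which label, reading or PHQ-9 score enters the primary test.

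The likely effect is small and has no direction between arms: somewhat inflated response rates in both and, usually, a slightly diluted contrast. In the assumed scenarios the 20% condition adds 0.1–2.7 points of power in five of six and 5.2 in the other (mean 15, r 0.6). The definitional statements follow from the text; the percentages rest wholly on assumed inputs. I would rate it between minor and should-fix: cheap to settle before unblinding, but not a threat to the trial's validity.

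**What to change.** Change the outcome definition only; eligibility and the stopping rule stay as they are.

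1. In Primary Outcomes, make the below-10 limb require improvement. One option: 'at least 50% reduction from baseline, or a score below 10 together with at least 20% reduction from baseline'. The 20% is borrowed from the protocol's continuation check and is one choice among several; it still accepts a 2-point fall at baselines 6–10. Another option is 50% reduction as primary, with below 10 as a secondary outcome.
2. Classify response at the last on-study post-baseline PHQ-9, and count patients with no post-baseline score as non-responders. The second clause is needed because Protection Against Risks allows early discontinuation and a staff form records withdrawals, so a later reading is not guaranteed.
3. Name the single PHQ-9 score used (AM, PM or a stated combination, and which items of the modified form), scored the same way at baseline.
4. In the Analysis Plan, state that this classification enters both the CMH test and the responder/non-responder comparison.
5. Reconcile the wording of Primary Outcomes, Procedures and the Analysis Plan by giving the 20% check its own label, such as 'insufficient early improvement'.

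The cost is a few sentences. The PHQ-9 is already scheduled at baseline and each session, so no new assessment is needed, provided the two forms can be scored alike. In the assumed scenarios, quoted response falls by 0.3–3.4 points in sham and 0.2–2.8 in TES with the 20% option. With 50% only, it falls by 3.0–15.2 and 3.8–12.9 points, and power slips from 67% to 66% in one scenario. Reading times will differ between patients, and the plan should say so.
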